2.1 Data Flow

An electronic data capture system, Medidata Rave, will be utilized for collection of study data. The Investigator will prepare and maintain adequate and accurate source documents designed to record all observations and other pertinent data for each subject who signs informed consent.

Study personnel at each site will enter data from source documents corresponding to a subject's visit or assessment into the protocol-specific electronic Case Report Form (eCRF). Subjects will not be identified by name in the study database or on any study documents to be collected by the Sponsor (or designee), but will be identified by a site number, subject number and initials. If a correction is required for an eCRF, the time and date stamp will track the person entering or updating eCRF data and creates an electronic audit trail.

The data will be entered into a validated database. The DCC will be responsible for data processing, in accordance with procedural documentation. All procedures for the handling and analysis of data will be conducted using good computing practices for the handling and analysis of data for clinical trials.

Once data have been entered into the study database, a system of computerized data validation checks will be implemented and applied to the database on a regular basis. Queries are entered, tracked, and resolved through the EDC system directly. The study database will be updated in accordance with the resolved queries. All changes to the study database will be documented in an audit trail.

2.2 Screening Spirometry

The study sites were permitted to use their spirometers with their proprietary reference equations to determine study eligibility per FEV₁ (% predicted) inclusion criteria. Because database randomization was built using the FEV₁ (liters) as an input to GLI equations to calculate percent of predicted FEV₁ for stratification, minor discrepancies in resulting % predicted values would potentially prevent some patients from participating in the study.

With this in mind, the lower limit of inclusion criteria (25-50% predicted) was lowered to 20% predicted (as determined by GLI equations) in the database. Because this change was limited to database randomization mechanism and did not affect study inclusion criterion, no protocol amendment was issued. The sites were asked to document all FEV₁ % predicted calculation discrepancies in the investigator log.

2.3 Report Generation

The final statistical report will describe and justify any deviations from the original statistical plan described herein. Analyses will be performed using SAS 9.4 software or most current version of

R. All programs used to produce this report will be documented, tested, and archived and all tables, figures and listings will be validated before considered final.

2.4 Data Sets Analyzed

All analyses will be performed using a modified intent-to-treat (m-ITT) population, which is defined as all randomized participants who received at least one dose of study drug. Participants who are discontinued from study drug temporarily or permanently are encouraged to complete all remaining study visits and will remain in the analyses population according to ITT. The primary efficacy analyses will be repeated in the per-protocol population, which is defined as participants having completed $\geq 80\%$ of doses (azithromycin and or placebo) and who did not require the use of acute antibiotics or steroids.

2.5 Definitions

Baseline – Baseline refers to Visit 1 (Day -14) when participants were randomized.

Study drug – During the randomized period, the study drug refers to the drug the participant was randomized to (either azithromycin or placebo). During the open-label period, the study drug refers to open-label azithromycin.

Treatment group – During the randomized period, the treatment group refers to participants randomized to either azithromycin or placebo. During the open-label period, the treatment group refers to participants either remaining on azithromycin or switching from placebo to azithromycin.

References

1. Emerson, SS and Fleming, TR. Symmetric group sequential test designs. *Biometrics*. 45:905-923, 1989.

Appendix A. Overview of Planned Analyses

A.1 Summary of Enrollment and Study Visit Completion

The cumulative enrollment of participants randomized into the study is graphically summarized. The number of participants screened, eligible, randomized, treated, withdrawn, and completing the study during the randomized period is summarized by both treatment group and site. Reasons for screen failure are summarized. Screen failures are participants that signed informed consent but did not meet eligibility criteria or chose not to participate in the study. The number of participants who withdrew early from the study is tabulated by treatment group and reason for withdrawal is summarized. Participant disposition figure detailing enrollment, treatment allocation, follow-up, and analyses populations is provided.

A.2 Demographics and Baseline Characteristics

Baseline demographics and clinical characteristics are descriptively summarized by treatment group and overall. Summarized characteristics include age, sex, CFTR genotype, race, height, weight, BMI, FEV₁ (liters and % predicted), delivery method of chronic tobramycin (i.e., dry powdered or inhaled), current use of chronic azithromycin, and use of other chronic medications. Fisher Exact tests are used to test at a two-sided 0.05 level of significance for differences in categorical variables across treatment arms. A two-sided t-test assuming unequal variance is used to test the difference between treatment arms for all continuous variables at a two-sided 0.05 level of significance.

A.3 Summary of Protocol Adherence Measures

The number of participants expected to have completed each visit and the number of participants who have missed a visit during the randomized period are summarized by treatment group. The follow-up time in the randomized period is summarized overall and by treatment group and also as the average time for each participant.

The proportion of participants who discontinued the study drug or experienced a dose modification during the randomized period is shown by treatment group. Reasons for drug discontinuation or other change to study drug regimen are also summarized.

Study drug compliance (azithromycin or placebo) is summarized in terms of the protocol defined treatment regimen during the randomized period. Compliance percentage is calculated for each participant as the number of doses reported taken divided by the number of doses expected (three 500 mg capsules per week over the six-week period, i.e. 18 doses), multiplied by 100. Also summarized is the compliance with TIS/TIP, calculated in a similar manner and assuming that the expected number of doses is 84 (inhaled twice daily over the six-week period). The average drug compliance is summarized in each treatment group. Also shown is the number and percentage of participants with $\geq 80\%$ compliance.

The number of participants included in the per-protocol population is provided by treatment group and reasons for exclusions are listed. Per-protocol population is defined as all randomized

participants having completed $\geq 80\%$ of doses of study drug (azithromycin or placebo) and who did not require the use of acute antibiotics or steroids.

A.4 Summary of Adverse Events

The safety population is used in all summaries of adverse events (AEs) and serious adverse events (SAEs). Note that all tables summarizing AEs also include SAEs (which are a subset of the AEs) unless otherwise specified.

According to our regulatory reporting criteria, a pulmonary exacerbation requiring a hospitalization results in an SAE (regardless of its expectedness). For the TDN trials, sites are asked to record the symptoms or physical findings associated with the pulmonary exacerbation as individual adverse events and to designate the seriousness of each of these events. Thus a single pulmonary exacerbation can be reported as several SAEs.

The incidence of AEs (including emergent abnormal QTc parameters) between the azithromycin and placebo treatment groups is tabulated by seriousness, severity, and relationship to study drug. The proportion of participants with at least one (S)AE, the average number of (S)AEs per patient, and the rate of (S)AEs per day of follow-up are reported. Poisson regression modeling is used to derive rate ratios and corresponding 95% confidence and to compare groups using a two-sided 0.05 level test. The difference in the proportion of participants experiencing at least one (S)AE between treatment groups is also reported, with corresponding 95% confidence intervals calculated using the Newcombe-Wilson method and p-values derived from a Fisher's exact test. Histograms showing the frequency of the number of (S)AEs in each treatment group are included.

All reported SAEs and AEs are coded using MedDRA and grouped by body system. Detailed summary tables of individual (S)AEs grouped by SOC are included to show the number and percent of participants experiencing each (S)AE by treatment group. The number and rate of events for each (S)AE is also reported by treatment group. Poisson regression is used to derive rate ratios and corresponding 95% confidence intervals comparing treatment arms for each SOC. Treatment groups are compared by the proportion of participants experiencing (S)AEs by System Organ Class (SOC) as well as the difference in proportions with corresponding 95% confidence intervals to compare treatment arms.

All SAE narratives are included in a listing appended to this report.

A.5 Summary of Spirometry Results

The primary endpoint is the difference between the azithromycin and placebo treatment groups in the relative change from Visit 1 to Visit 3 in FEV1 (liters). The primary efficacy analysis is conducted on the m-ITT population and repeated on per-protocol population. Predicted values for spirometry measures at each visit are calculated using the Global Lung Initiative reference equations.

A linear regression model adjusted for randomization strata is used to compare the primary endpoint between treatment groups. Least squares means and the treatment effect are presented

along with corresponding 95% confidence intervals and p-values. The primary analysis is adjusted for the group sequential monitoring.

The primary endpoint is also summarized descriptively as a plot of average values in each treatment group at each post-randomization visit accompanied by 95% confidence intervals (using t-distribution approximation).

Additional secondary analysis may be performed to adjust for potential baseline confounders including age, sex, use of CFTR modulators, and baseline FEV1. To address missing data, the least favorable treatment arm imputation method is used to impute that missing value with the mean change from the treatment arm with the worst change in the observed case analysis. In further sensitivity analyses, the primary endpoint is summarized for a select number of baseline covariates including age, sex, baseline FEV1, chronic azithromycin use, and inhaled tobramycin formulation.

The exploratory spirometry endpoints, i.e. absolute change from Visit 1 to Visit 3 in FEV1 (liters and % predicted), absolute and relative change in FVC (liters and % predicted), and absolute and relative change in FEF25-75% are summarized descriptively as plots of mean values and corresponding 95% confidence intervals over time.

Additionally, changes in spirometry measures from Visit 1 to Visit 3 and Visit 2 to Visit 3 are modeled using linear regression adjusted for randomization strata. The estimates of least squares means, differences in the least squares means between the treatment groups, and corresponding 95% confidence intervals and p-values are presented.

All of the spirometry measures are summarized at each study visit during the randomized period and as a change from Visit 1 and Visit 2. The differences between treatment groups are presented with accompanying 95% confidence intervals and p-values calculated using two-sample t-tests.

Post-hoc comparisons of participants responding and not responding to monotherapy are summarized. Several 'responder' definitions are considered, e.g. XX% or greater relative increase in FEV1 % predicted from Visit 1 to Visit 3, XX% or greater relative increase in FEV1 % predicted from Visit 2 to Visit 3, 11 or greater point decline in CFRSD-CRISS from Visit 1 to Visit 3, and a XX point increase in CFQ-R respiratory symptom scale.

A.6 Pulmonary Exacerbations, Hospitalizations and Antibiotic Usage

The number of pulmonary exacerbations and hospitalizations is descriptively summarized. Proportions of participants initiating intravenous, inhaled, and oral antibiotics during randomized period are also presented. The differences in the proportions of participants experiencing at least one event between treatment groups are estimated with accompanying 95% confidence intervals calculated using the Newcombe-Wilson method and p-values derived from a Fisher's exact test.

A.7 Summary of Weight

Mean changes in weight (kg) from Visit 1 to each post-randomization visit for both treatment groups during the randomized period are summarized descriptively in a figure. 95% confidence intervals (using t-distribution approximation) are included at each time point. The number of participants at each time point is included in a legend below the figure.

A linear regression model adjusted for randomization strata is used to compare changes in weight (kg) between treatment groups. Least squares means and the treatment effect are presented along with corresponding 95% confidence intervals and p-values.

The weight (kg) is also summarized at each study visit during the randomized period and as a change from Visit 1 and Visit 2. The differences between treatment groups are presented with accompanying 95% confidence intervals and p-values calculated using two-sample t-tests.

A.8 Summary of Patient-Reported Quality of Life Measures

Mean changes in CFRSD-CRISS and CFQ-R Respiratory Symptom Scale (RSS) from Visit 1 to each post-randomization visit for both treatment groups during the randomized period are summarized descriptively in figures. 95% confidence intervals (using t-distribution approximation) are included at each time point. The number of participants at each time point is included in a legend below the figures.

Linear regression models adjusted for randomization strata are used to compare changes in CFRSD-CRISS and CFQ-R RSS between treatment groups. Least squares means and the treatment effect are presented along with corresponding 95% confidence intervals and p-values.

CFRSD-CRISS and CFQ-R RSS are also summarized at each study visit during the randomized period and as a change from Visit 1 and Visit 2. The differences between treatment groups are presented with accompanying 95% confidence intervals and p-values calculated using two-sample t-tests

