
DURATION OF SUBJECT PARTICIPATION AND DURATION OF STUDY
	
Subjects will be enrolled in the randomized study for up to 42 days (6 weeks).
 
 
• Treatment V1-V2: azithromycin or placebo without TISP: 14 days (-2 days/+4 days) followed by:
 
• Treatment V2-V3: azithromycin or placebo with TISP: 28 days (-2 days/+4 days)
 
 
Subjects participating in the optional open-label extension will be on study for up to 98 days (14 weeks).
 
 
• Treatment V3-V4: azithromycin without TISP: 28 days (-/+4 days) followed by:
 
• Treatment V4-V5: azithromycin with TISP 28 days (-/+4 days)
 
 
The total duration of the study is expected to be approximately 33.5 months: 30 months for subject recruitment and 3.5 months for the final subject enrolled to complete the study.

PRIMARY OBJECTIVE
	
Determine if azithromycin impairs the previously-recognized clinical benefits of inhaled tobramycin by comparing changes in pulmonary function as measured by FEV1 between subjects randomized to azithromycin versus placebo.

SECONDARY OBJECTIVES	
The secondary objectives for the randomized period are to:
 
 
• Compare changes in patient-reported quality of life between subjects randomized to azithromycin versus placebo
 
 
The secondary exploratory objectives for the randomized period are to:
 
 
• Compare the safety profile between subjects randomized to azithromycin versus placebo
 
• Compare changes in additional spirometry measures, bacterial density, and weight between subjects randomized to azithromycin versus placebo
 
• Compare rates of pulmonary exacerbations, hospitalizations, and acute antibiotic usage between subjects randomized to azithromycin versus placebo
 
 
The objectives for those continuing in the open-label extension:
 
 
• Among those randomized to azithromycin and remaining on azithromycin, obtain additional data to determine the long term effect of azithromycin on clinical outcomes
 
• Among those randomized to placebo and switching to azithromycin, compare differences in clinical outcomes observed during the randomized and open-label periods
 

NUMBER OF SUBJECTS	
Approximately 120 subjects randomized

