### 8.4.3 Packaging and Labeling

Capsules for the randomized period of the study will be provided in labeled bottles. A six-week supply plus one extra (19) of capsules will be included in each bottle. One bottle will be supplied at Visit 1.

If the subject enrolls in the open-label period, commercially-available azithromycin will be provided by the site pharmacy.

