### 8.6 Dose Modifications

#### 8.6.1 Due to Toxicity

If a study subject has moderate to severe toxicity (refer to Study Manual), the following schedule for dosage adjustment can be made at the discretion of the site investigator:

- If a study subject receiving study drug three times weekly (TIW) experiences drug-related toxicity, the dosing INTERVAL of the study drug will be extended to two times weekly (BIW; e.g., Monday and Thursday)
- If a study subject does not tolerate receiving study drug BIW, the subject should be permanently discontinued from study drug due to intolerance.

Dose can return to TIW at the discretion of the site investigator.

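### Study-drug compliance is scored against a fixed 18 doses, which misplaces participants near the 80% per-protocol cut-off when visit dates or required holds change the number of doses due

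*SAP*

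**What the plan says.** SAP A.3 says that study-drug compliance "is summarized in terms of the protocol defined treatment regimen during the randomized period". The percentage is doses reported taken over doses expected, and doses expected is a constant: "three 500 mg capsules per week over the six-week period, i.e. 18 doses". The same section defines the per-protocol population as participants with at least 80% "of doses of study drug (azithromycin or placebo) and who did not require the use of acute antibiotics or steroids".

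The Protocol Synopsis gives the nominal length: "Subjects will be enrolled in the randomized study for up to 42 days (6 weeks"). It then puts a window on each of the two intervals: "Treatment V1-V2: azithromycin or placebo without TISP: 14 days (-2 days/+4 days") and "azithromycin or placebo with TISP: 28 days (-2 days/+4 days").

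Three other protocol provisions bear on how many doses a participant can or should take:

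- Section 8.4.3, on supply: "A six-week supply plus one extra (19) of capsules will be included in each bottle". One bottle is given, at Visit 1.
- Section 8.6.1, on drug-related toxicity: "the dosing INTERVAL of the study drug will be extended to two times weekly". Return to three times weekly is left to the site investigator.
- Section 7.2 makes a temporary stop of study drug mandatory during acute macrolide treatment and during acute use of some QT-prolonging drugs.

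Neither document says how the 18 is adjusted for off-nominal visit dates, required holds or the twice-weekly schedule.

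**The concern.** The number 18 is right for a participant who attends exactly on schedule and is never held or moved to a reduced schedule. For others the number of doses due differs, but the divisor does not. Someone seen early can take more than 80% of the doses due and be scored below 80%. Someone seen late can take fewer than 80% of those due and be scored above it. A participant whose drug is stopped because the protocol requires it loses the held doses as if they had been missed.

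What is at stake is membership of the per-protocol set, in which the primary FEV1 analysis is repeated. That set is meant to show the result in people who took the assigned treatment as planned, so the adherence rule should measure adherence and not visit timing.

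**Working it through.** **Inputs.** Three doses a week and six weeks (SAP A.3); 80% threshold (SAP A.3); intervals of 14 and 28 days, each -2/+4 days (Protocol Synopsis); 19 capsules (Protocol 8.4.3); twice-weekly option (Protocol 8.6.1); required holds (Protocol 7.2). One assumption is mine: a Monday-Wednesday-Friday pattern for the calendar counts. The documents do not fix the days for three-times-weekly dosing.

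**The plan's own figures.** 3 × 6 = 18, as stated. 18 + 1 = 19, which agrees with the supply. The threshold is 0.80 × 18 = 14.4, so a participant needs at least 15 doses.

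**Length of the randomized period.** Using both interval windows: (14 − 2) + (28 − 2) = 38 days and (14 + 4) + (28 + 4) = 50 days. If Visit 3 is instead held to Day 28 of the nominal schedule: 42 − 2 = 40 and 42 + 4 = 46 days.

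**Doses due before Visit 3.**

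| Days | 3 × days / 7 | Calendar count |
|---|---|---|
| 38 | 16.3 | 16–17 |
| 40 | 17.1 | 17–18 |
| 42 | 18.0 | 18 |
| 46 | 19.7 | 20 |
| 50 | 21.4 | 22 |

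**Who is misplaced.** These are the counts for which the fixed rule and the doses-due rule disagree.

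| Due | Taken | % of due | % of 18 | Fixed rule |
|---|---|---|---|---|
| 16 | 13 | 81% | 72% | excluded |
| 16 | 14 | 88% | 78% | excluded |
| 17 | 14 | 82% | 78% | excluded |
| 18 | none | – | – | – |
| 20 | 15 | 75% | 83% | included |

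The last row also stands against the capsules available: 15/19 = 79%, still below 80%. At 50 days, 22 doses fall due but only 19 can be taken. Measured against 19, only a participant with exactly 15 doses is misplaced at the long end, since 16/19 = 84%.

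**Full adherence, no holds.** At 38 days at least 16/18 = 89%; with all 19 capsules taken, 19/18 = 106%. Both pass.

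**Required holds.** If four doses of 18 are held and the other 14 are all taken, the score is 14/18 = 78% and the participant is excluded, having taken 14/14 of the doses due. For macrolides this changes nothing, because acute antibiotic use already excludes. It matters when the drug that requires the hold is neither an antibiotic nor a steroid.

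**Twice-weekly schedule.** A switch after w full weeks, kept to week six, gives 3w + 2(6 − w) = 12 + w doses. For w = 0, 1, 2 this is 12, 13 and 14 doses: 67%, 72% and 78% of 18, all below 80%. From w = 3 it is 15/18 = 83% or more.

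**Supply against windows.** With the first dose on day 0, a Monday, 18 doses are taken in the first six weeks and the 19th on day 42. Doses then fall due on days 44, 46 and 49, so up to three are uncovered before a Visit 3 on day 50. Protocol 4.1 and SAP 1.1 both have study-drug dosing continue up to Visit 3.

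**The case against.** The strongest reply is that 18 is correct for the nominal regimen, that A.3 says openly that compliance is measured against the protocol-defined regimen, and that the primary analysis uses the modified intent-to-treat population. All of that stands. It limits the point to participants near the cut-off in one sensitivity analysis. It is also an inference, though the natural one, that the A.3 percentage is what the 80% rule uses. No other denominator appears in either document.

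Several stronger readings are tempting and are not supported:

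- **That 19 capsules contradict 18 doses.** The bottle is defined as the six-week supply plus one extra, which confirms 18. The tension is only between the supply and the long end of the windows.
- **That 15 doses over 50 days is 68% true compliance (15 of 22).** Three of those 22 doses could not be taken from a 19-capsule bottle. Against the supply it is 79%.
- **That leaving out reduced-schedule participants is an error.** A per-protocol set limited to near-full exposure is a legitimate choice. What is missing is a statement that this is intended. The case is also narrow: the switch must come within the first two weeks and persist.
- **That azithromycin participants would be excluded more often.** This is at most an unquantified possibility. The documents give no rate of early switching in either arm, and inclusion criterion 11 requires current or prior chronic azithromycin use, which may make new intolerance less likely. A.3 also plans per-protocol counts by arm with reasons for exclusion, so an imbalance would be visible.

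**Conclusion.** The point holds in a limited form. A fixed 18 misplaces participants who take 13 or 14 doses over a short period or 15 over a long one, and those near the cut-off after a required hold. It does not exclude anyone who takes every three-times-weekly dose without a hold. The primary analysis is unaffected.

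The number of people involved cannot be computed, because the documents do not give the spread of actual visit intervals, the frequency of holds or the frequency of twice-weekly dosing. The 38-to-50-day range takes both windows at the same extreme. Under the narrower 40-to-46-day reading the over-scoring at 46 days remains, and the under-scoring remains where 17 doses fall due at 40 days. The calendar counts and the day-42 run-out rest on the assumed weekly pattern.

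The shortfall in supply at a late Visit 3 is a separate inconsistency between protocol passages. This is a minor but worthwhile correction.

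**What to change.** In SAP A.3, define expected doses for each participant as the three-times-weekly doses due from first dose to the actual Visit 3, less doses withheld under a protocol-required hold, and not more than the capsules supplied. State whether a dose due on the visit day counts. Apply the 80% rule to that figure, and keep the percentage of 18 as a descriptive measure of exposure. The cap matters: without it, 17 of 19 capsules over 50 days would score 17/22 = 77% and be excluded for a supply limit.

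Add one sentence on whether participants on the permitted twice-weekly schedule are meant to be in the per-protocol set. If any occur, show the per-protocol result with and without them.

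The cost is a few SAP sentences, settled before unblinding. Diaries, pill counts, visit dates, concomitant medications and dose modifications are already recorded. The drawback is a slightly more complex derivation and, if reduced-schedule participants are admitted, a set with somewhat lower exposure.

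Separately, Protocol 8.4.3 and the visit windows must be reconciled with dosing up to Visit 3. How to do so is for the trial team.
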